4 LOCAL AND STUDY-WIDE NUMBER OF SUBJECTS

4.1 Total Number of Subjects to be Accrued Across All Sites.

We will conduct this study with current cigarette smokers (100 in Buffalo, 100 in Boston, 100 in Charleston) for a total N of 300. We hope to achieve N=240 with complete data. An equal number of males and females will be recruited for the study at each site.

Stratified recruitment scheme for Study 3.1		
	Cigarette Smoker	
Sex	M	F
Overall N	150	150
Buffalo	50	50
Boston	50	50
Charleston	50	50

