11.2 Treatment

This study will use two types of cigarettes. One set of cigarettes are commercially available Marlboro cigarettes (Philip Morris USA, Richmond, VA), all combustible King size (83mm) cigarettes consisting of filler, filter paper, tipping paper, cigarette paper, tipping glue and seam glue. Specific varieties are listed in the table. Products will be sourced at retail from local outlets.

Alternatively, participants may receive investigational “roll your own” (RYO) cigarettes that will be prepared in the laboratory. These cigarettes will be made to match the commercially available Marlboro cigarettes. These cigarettes will be prepared with conventional tobacco (e.g., Good Stuff) rolled using an automatic rolling machine (e.g., Powermatic III+) and packaged into 20 rod packs. The investigational RYO cigarettes will use ventilated filter tubes (e.g., ~25-37% filter ventilation). The dose of nicotine in these RYO cigarettes will be similar to conventional cigarettes.

Within each pair of products is a nonmenthol and menthol equivalent. Participants who report regularly smoking menthol cigarettes will receive the menthol versions for the study.

Variety	Vent %	Filter length (mm)	Tobacco weight (mg)
Special Blend Smooth Mellow	30.6	27	625.1
Smooth Fresh Menthol	37.6	27	630.8

Additionally, cigarettes will be paired with messaging about filter ventilation. This message will be affixed to the front exterior of each package provided to participants.

- No Message (e.g., unaltered cigarette pack).
- Neutral Message: “Nothing about this product’s color or name means that it will protect a smoker from the health risks of smoking.”
- Compensation Message: “This product has a ventilated filter. Filter vents increase how deeply a smoker inhales without them knowing, which can increase the health risks of smoking.”
- Blocking Message: “This product has a ventilated filter. Be sure not to block the vent holes with your fingers or lips, which can increase the health risks of smoking.”

Roswell Park Protocol Number: I 757820

With these conditions, ‘no message’ serves as a true control (smoking as normal), while the neutral message serves as a control message to determine if added messaging impacts behavior/perceptions, even if that message is not informational. The compensation and blocking messages will determine if added messaging about the health risks of filter ventilation affect behavior/perceptions, and which type of message has the greater impact.

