In the event of REDCap being inaccessible for a study visit, .pdf files or paper copies of the consent will be provided to the participants and the participants will be able to sign and return or submit a photo of the signed copy.

The participant will then be randomized to 1 of 4 message conditions (No message, Neutral message, Compensation message, Blocking message) and arrangements will be made to mail, deliver, or have participants pick up study materials (study cigarettes with pack messages, CO

Roswell Park Protocol Number: I 757820

monitor, scales, butt collection materials, shipping materials, etc.). Participants will be provided with two weeks of materials.

Session 1. Session 1 will occur upon receipt of study materials by the participant. Participants will complete a baseline intake questionnaire including smoking and tobacco use history, nicotine dependence scales, SCQ, TRIRISK, delay discounting, respiratory symptoms, and knowledge, attitudes, and beliefs about filter vents. In addition, participants complete questionnaires on message perceptions (response to messaging, health risk, purchase intention) for all pack messages. Questionnaires also will be used to get baseline assessments of the user's usual brand of cigarettes (Duke Sensory Scale, Product Evaluation Scale, Hedonic Attribute Scale). Participants will be instructed to record each smoking event using the EMA app provided (described in more detail below) and to retain all spent cigarette butts and unused product. Participants will be informed that they are free to use other tobacco products (though they will not be provided as part of the study), and that these should be recorded using EMA. Participants will be provided for cigarettes for a total of two weeks, with the amount determined by normal self-reported weekly consumption rounded to nearest whole pack.

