22 STATISTICAL PLAN

22.1 Data Analysis Plan

The analysis of EMA data will be analyzed using a linear mixed model with fixed effects for vent message (product design, color/name), as well as sex and other tobacco product strata (cigarettes only or dual use). The effect of packaging will be tested using a Bonferroni-corrected type-I error rate of 0.008 (0.05/6) to account for all possible pairwise comparisons of packaging types. Data from the field-study (e.g., change in product responses, risk, TNE, aldehyde-DNA adducts) will be analyzed using linear regression with terms in the model for vent message (no message, neutral, compensation, blocking), sex, and other tobacco product use.. Categorical outcomes for the field-study will be analyzed using logistic regression. As exploratory approaches, we will use time-varying effects models (TVEMs) to explore the effect of message condition on smoking behavior (product compliance), craving, risk perception, and quit intention in the EMA data.[191, 192] TVEMs have been used previously to examine treatment effects on craving [193] and relapse.[194] TVEMs will provide daily effect sizes, thereby allowing us to examine whether treatment effects (and relationships with other predictors) change over time (i.e., early vs. later in product switching). Responses at Visit 1 can be treated as time invariant predictors and mCEQ from EMA can be treated as time-varying predictor (and/or outcome) of product use.

Roswell Park Protocol Number: I 757820

We will enroll a total sample size of 300 subjects and assume a 20% drop-out rate with uniform drop-out from Visit 1 to Visit 3. This will result in a sample size of 300 subjects for Visit 1, 270 subjects for the first week of the field study, and 240 subjects for the end of field study. Our sample size was determined to have adequate power for the field study, For the field study, we hypothesize a 25% difference between conditions, corresponding to a 3.9 CPD difference. Assuming a standard deviation of 7.6,[195] a sample size of 240 subjects will provide 95% power to detect a significant difference between ventilation conditions at the 0.05 level and 80% power to detect a significant difference between packaging conditions with a Bonferroni-corrected type-I error rate of 0.008.

mCEQ is scored using an established algorithm.⁹⁶ This results in 3 subscales (Psychological Reward, Relief, Reward) and 2 single items (Aversion, Respiratory sensation). Scores range from 1-7.

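### Recruitment quotas are set by site and sex, but the two linear models in section 22.1 omit site, at a modest cost in precision

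*Combined protocol and SAP*

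**What the plan says.** Section 4.1 sets equal site quotas, "100 in Buffalo, 100 in Boston, 100 in Charleston", and adds that "An equal number of males and females will be recruited for the study at each site". Its table, headed "Stratified recruitment scheme for Study 3.1", shows 50 men and 50 women at each site.

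Section 11.3 describes allocation in one sentence: "The participant will then be randomized to 1 of 4 message conditions". It names no allocation ratio, blocking or stratification factor.

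Section 22.1 analyses the EMA data with a mixed model that has a fixed effect for the message, "as well as sex and other tobacco product strata (cigarettes only or dual use"). The field-study linear regression has "terms in the model for vent message (no message, neutral, compensation, blocking), sex, and other tobacco product use". Neither list contains site as a fixed or random effect, and nothing elsewhere in the plan adds it. For the logistic models and the time-varying effects models, no adjustment covariates are listed.

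**The concern.** The design has two recruitment strata. The linear models keep sex and drop site, and no reason is given. The sites could differ in outcome level because each recruits through local advertising and networks (section 6.1.1) and writes to its own former participants (section 8.2).

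If they do differ, the variation has nowhere to go but the error of the message contrasts; in the mixed model, that is the between-participant variance. The outcomes most exposed are those analysed as levels, such as cigarettes smoked during the field period, which is a primary endpoint. At stake is some power in a comparison that has little to spare, and a choice between adjusted and unadjusted results that would otherwise be made after the data are seen.

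**Working it through.** **Inputs.** From section 22.1: difference 3.9 CPD, SD 7.6, 240 completers, pairwise alpha 0.05/6 = 0.0083. Assumed, because the documents do not say: equal allocation (240/4 = 60 per arm), a two-sided test, and the site share of variance, s, taken as 1%, 5% or 10%.

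**1. The plan's own figure.** SE = 7.6 × √(2/60) = 1.388 and noncentrality = 3.9/1.388 = 2.81. Noncentral t power on 118 df is 55.2% (56.8% by normal approximation). The stated 80% does not reproduce. That is a separate matter; 55.2% serves here only as the starting point.

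**2. Gain from a site term under simple randomisation.** Take three sites of 80 completers with random site effects.

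- Without site, the contrast variance is proportional to (1 − s) + 0.669s. The factor is 80 × 2/239 = 0.669, because three sites realise on average only about two thirds of the assumed site variance.
- With site, it is proportional to (1 − s) × (1 + 2/236) = (1 − s) × 1.0085. The second factor is the approximate price of estimating two more terms when arms are not balanced within site.

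| s | With site | Without site | Ratio | Pairwise power |
|---|---|---|---|---|
| 1% | 0.998 | 0.997 | 1.00 | 55.2% |
| 5% | 0.958 | 0.983 | 0.97 | 56.9% |
| 10% | 0.908 | 0.967 | 0.94 | 58.6% |

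Power uses SE = 1.388 × √ratio, which is 1.367 at a ratio of 0.97 and 1.345 at 0.94. Simulations of this set-up gave ratios of about 1.00, 0.97 to 0.98, and 0.93 to 0.94. The gain is therefore 0 to about 4 points.

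**3. Upper limit.** Replacing the SD by 7.6 × √(1 − s) treats adjustment as free and assumes that the three sites realise exactly the assumed share. It gives SDs of 7.41 (5%) and 7.21 (10%), and power of 58.0% and 61.1%. These are ceilings rather than expected gains.

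**4. If allocation is stratified by site.** The arms are then balanced within site, so site adds nothing to the true contrast variance. The unadjusted model still includes it in the SE. If the realised share equals s, the SE is too large by 1/√(1 − s). The effective critical value is 1.96/√0.95 = 2.011 at 5% and 1.96/√0.90 = 2.066 at 10%, so true type I error is about 4.4% and 3.9% at a nominal 5%. Simulations ranged from 3.7% to 4.6%.

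**The case against.** The strongest reply is that nothing here is invalid. Section 4.1 sets recruitment quotas and does not describe stratified randomisation. Participants are randomised individually, so leaving out site neither biases the linear contrasts nor inflates type I error. This stands: the point concerns efficiency.

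The evidence for large site differences is also thin. On the commercial cigarettes, section 11.2 says "Products will be sourced at retail from local outlets", but it names fixed varieties with tabulated ventilation, so local purchase need not make the product differ. Sessions are remote (section 6.1.2), data go into one REDCap database (section 19.3), and Appendix D supplies a common experimenter script. The SD of 7.6 may already include site variation. This stands too, and is why a 1% share, with no gain, belongs in the range.

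Four stronger readings are tempting, and the documents do not support them:

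- *Every arm comparison is affected.* Section 22.1 speaks of change in product responses, and stable site differences in level largely cancel in change scores. Logistic models have no residual error term; there, an omitted site effect attenuates the odds ratio.
- *Residual variance and chance imbalance are two losses.* Under simple randomisation an arm's share of a site's 100 enrolled has mean 25 and SD √(100 × 0.25 × 0.75) = 4.3. Site variance enters an unadjusted contrast only through that imbalance, so the two are one mechanism.
- *The models adjust for sex alone.* Sex is the only recruitment stratum retained, but other tobacco use is also a term.
- *The omission explains the power shortfall.* By normal approximation, a site share of about 35% would be needed to reach 80%.

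What survives is that a known design stratum is left out of two fully listed linear models without a reason, and that including it is nearly free.

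**Conclusion.** The point holds as a modest loss of precision in the message contrasts of the EMA mixed model and the field-study linear regression, mainly for outcomes analysed as levels. At assumed site shares of 1%, 5% and 10%, the expected reduction in contrast variance from adjustment is about 0%, 3% and 6%. These figures rest on equal arms, a two-sided test, three equal sites and a site variance that the documents do not supply. If the list is stratified by site, the consequence is instead a mildly conservative test. Because section 11.3 does not say which scheme applies, the plan should state it. Neither case threatens validity. The change is worth making because it is cheap and settles the covariate set in advance.

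**What to change.** - In section 22.1, add site (three levels) as a fixed effect to the EMA mixed model and the field-study linear regression.
- State that the logistic models use the same covariates: site, sex and other tobacco use.
- In section 11.3, state how allocation is done. If the randomisation list can still be set, block the four arms within site and sex. If it cannot, record the scheme that was used.

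The cost is a few lines of text, possibly a setting in the randomisation list, and two degrees of freedom out of about 240 participants. If site accounts for about 1% of the variance or less, there is no gain in precision. Odds ratios from the logistic models would then be conditional on site, which the report should say. The sample size justification needs its own correction.

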11.3 Study Procedures

The proposed study is a between-subjects design in which participants will be randomized to 1 of 4 conditions for 2 weeks.

- No Message (e.g., unaltered cigarette pack).
- Neutral Message: “Nothing about this product’s color or name means that it will protect a smoker from the health risks of smoking.”
- Compensation Message: “This product has a ventilated filter. Filter vents increase how deeply a smoker inhales without them knowing, which can increase the health risks of smoking.”
- Blocking Message: “This product has a ventilated filter. Be sure not to block the vent holes with your fingers or lips, which can increase the health risks of smoking.

Data will be collected in three remote video sessions and via EMA conducted over 2 weeks. Each study session is expected to take 0.5 hours. For each condition, active data collection is expected to take no more than 15 minutes. Study materials (cigarettes, CO monitor, containers for cigarette filter collection, scales) will be mailed to, delivered, or picked up by participants. Session 1 will involve confirmation of receipt of study materials, questionnaires, and training on procedures. Then, participants will track their product use via EMA app (REDCap) for 2 weeks, with two remote sessions via videoconference for additional questionnaires.

Informed Consent. An initial videoconferencing session will be used for informed consent. Consent will be obtained through the REDCap (Research Electronic Data Capture) system used for data collection. REDCap is a secure web-based application that supports data capture and management for research studies. The Investigator and Research Associate will design the study specific consent and upload the most recent CRS versions to the REDCap system. A secure link will be sent to each participant prior to the start time of the study. Research staff will guide the participant form, provide time to read the consent, and answer any questions. Participants and staff will be able to electronically sign, data, and submit the consent in real-time. Once the consent is submitted, it is automatically saved on RPCI protected servers. Access to this folder is restricted to authorized users. Standard protocols for data encryption (via Credant) when using laptops and USB drives will be followed.

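### The six message comparisons use single-step Bonferroni at 0.008, which is valid but conservative; a Holm-type or Tukey-Kramer test would add a few points of per-pair power for one sentence of text

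*Combined protocol and SAP*

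**What the plan says.** Section 11.3 sets out four parallel arms: "The proposed study is a between-subjects design in which participants will be randomized to 1 of 4 conditions for 2 weeks". Four arms give 4 × 3 / 2 = 6 pairs.

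Section 22.1 attaches a multiplicity rule to the mixed model for the EMA data: "The effect of packaging will be tested using a Bonferroni-corrected type-I error rate of 0.008 (0.05/6"). This is one fixed threshold for every pair, and its stated purpose is "to account for all possible pairwise comparisons of packaging types". It calls the conditions packaging types. The divisor of six shows that the four message conditions are meant. No step-down or Tukey-type method is mentioned, and no reason is given for choosing Bonferroni.

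The power statement in the same section uses the same threshold. It claims "80% power to detect a significant difference between packaging conditions with a Bonferroni-corrected type-I error rate of 0.008".

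Section 11.2 explains why the family covers more than the comparisons with control. The two informational messages are also to be compared with each other, to learn "and which type of message has the greater impact". Keeping all six pairs therefore fits the design.

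**The concern.** Single-step Bonferroni treats the six tests as if nothing were known about how they relate. In fact they share arms, so the test statistics are correlated. They are also logically linked: if one pair differs, at most three of the remaining equalities can all be true. Tukey's method uses the correlation, Shaffer's version of Holm uses the logic, and plain Holm needs neither. Each keeps family-wise control at 5% for the same six pairs.

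At stake is efficiency. Power for a single pair is modest at the planned size, and Section 11.2 wants to know which messages differ from which, so extra per-pair power that costs no participants is worth having.

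**Working it through.** **Inputs.** From Section 22.1: a difference of 3.9 CPD ("we hypothesize a 25% difference between conditions, corresponding to a 3.9 CPD difference"); SD 7.6 and 240 analysed ("Assuming a standard deviation of 7.6,[195] a sample size of 240 subjects"); level 0.008. From Section 11.3: four arms. Assumed, because the documents do not say: equal allocation (240 / 4 = 60 per arm), two-sided tests, and one independent CPD mean per participant with common variance.

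**The plan's own figure.** The standard error of a pairwise difference is 7.6 × √(2/60) = 1.388, so the standardised shift is 3.9 / 1.388 = 2.811. At two-sided 0.008 the power for one pair is 56.3% (normal approximation) or 54.7% (two-sample t), not 80%. With 60 per arm, 80.2% appears at an unadjusted 0.05 (normal approximation).

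**Single-step thresholds** with the pooled variance (240 − 4 = 236 df). Power is roughly Φ(2.811 − critical t); the values below come from the noncentral t.

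| Rule | Critical t | Per-pair power |
|---|---|---|
| Bonferroni at 0.008 | 2.675 | 55.5% |
| Bonferroni at exact 0.05/6 | 2.661 | 56.0% |
| Tukey (per-comparison level 0.0103) | 2.587 | 58.9% |

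About half a point is lost simply by rounding 0.00833 down to 0.008. For 80% per-pair power, 93 per arm are needed with Bonferroni at 0.008 and about 89 with Tukey.

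**Step-down tests.** These depend on all four means, so they were simulated (200,000 trials per pattern; simulation error about 0.1 point). The ordered p-values are compared with 0.05 divided by 6, 5, 4, 3, 2, 1 (Holm) or by 6, 3, 3, 3, 2, 1 (Shaffer).

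Power for a pair that differs by 3.9 CPD (%):

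| True means | 0.008 | Holm | Shaffer-Holm | Tukey |
|---|---|---|---|---|
| 0, 0, 0, 3.9 | 55.5 | 58.9 | 62.7 | 58.9 |
| 0, 0, 3.9, 3.9 | 55.5 | 60.9 | 63.7 | 58.9 |
| 0, 0, 1.95, 3.9 | 55.6 | 58.2 | 61.5 | 59.0 |
| 0, 1.95, 1.95, 3.9 | 55.2 | 56.4 | 57.6 | 58.6 |

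In a further run of 100,000 trials with evenly graded means (0, 1.3, 2.6, 3.9), Holm gave 57.0% and Shaffer-Holm 58.8%.

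Chance of at least one true rejection (%):

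| True means | 0.008 | Holm | Shaffer-Holm | Tukey |
|---|---|---|---|---|
| 0, 0, 0, 3.9 | 79.6 | 80.0 | 80.1 | 82.3 |
| 0, 0, 3.9, 3.9 | 87.1 | 87.4 | 87.4 | 89.2 |
| 0, 0, 1.95, 3.9 | 74.1 | 74.6 | 74.6 | 77.2 |
| 0, 1.95, 1.95, 3.9 | 60.1 | 60.7 | 60.8 | 63.8 |

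The step-down gain of about half a point here is the rounding of 0.05/6, because the first step of Holm and of Shaffer is Bonferroni.

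The chance of finding every true difference moves more. With one arm different it is 30.5% at 0.008, 36.9% with Holm, 41.5% with Shaffer-Holm and 34.0% with Tukey. With two arms against two it is 21.6%, 31.7%, 32.1% and 24.9%.

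Family-wise error (%):

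| True means | 0.008 | Holm | Shaffer-Holm | Tukey |
|---|---|---|---|---|
| all equal | 4.0 | 4.2 | 4.2 | 5.0 |
| 0, 0, 0, 3.9 | 2.2 | 3.3 | 4.3 | 2.8 |
| 0, 0, 3.9, 3.9 | 1.6 | 2.8 | 3.5 | 2.1 |

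**The case against.** The strongest reply is that nothing here is broken. 0.05/6 is the right division for four arms, the rule is prespecified, and it carries over unchanged to any model that yields p-values, including the logistic models in Section 22.1. That stands: the point concerns efficiency, not validity.

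A second reply also stands. A reader might infer that the change is free and that Bonferroni's caution buys nothing. Neither is so. Step-down tests lack simple simultaneous intervals, and Sections 1.2 and 11.1 expect no effect on smoking behaviour, so intervals that bound a CPD difference may matter more than extra rejections. Tukey-Kramer keeps the intervals, but it is only approximate in a covariate-adjusted mixed model with unequal dropout. Bonferroni's lower actual error, 2.2% against 4.3% for Shaffer-Holm when one arm differs, is real extra protection, even though both are within 5%.

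Third, the 4.0% error when all arms are equal is an argument for Tukey only. Holm and Shaffer-Holm stand at 4.2% there; their gain comes at the later steps.

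Fourth, Section 22.1 does not say whether its 80% refers to a given pair or to any pair. On the any-pair reading with one arm different, the plan already reaches 79.6% and step-down testing adds almost nothing. That holds for that one pattern; over the four patterns the figure runs from 60.1% to 87.1%.

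**Conclusion.** The plan's rule is valid and somewhat conservative, and a better rule for the same six pairs is available cheaply. Over 0.008, the per-pair gain for a 3.9 CPD difference is about 3.4 points with Tukey, 1 to 5 with Holm and 2 to 8 with Shaffer-Holm. The larger step-down gains arise when the means form two clusters. With evenly graded means, or two arms midway between the extremes, step-down testing gains about 1 to 3 points and Tukey does as well or slightly better.

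A reader might go further and conclude that Section 22.1 contains a multiplicity error, or that a sharper procedure would rescue the stated 80%. The documents support neither. The family-wise error is controlled, and per-pair power reaches at most about 64% under any of these rules. The gap between that and 80% is a sample-size question to be settled separately.

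The figures rest on equal arms of 60, two-sided tests, common variance and one CPD mean per participant. The mixed-model results will differ somewhat.

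**What to change.** Replace the fixed 0.008 threshold in Section 22.1 with one sentence, for example: the six pairwise message contrasts from the mixed model will be tested with Holm's procedure (or Shaffer's modification of it) at a two-sided family-wise level of 0.05. If simultaneous confidence intervals will be reported, name Tukey-Kramer adjustment instead. Keep all six pairs. Choose one method and record it before any comparison by arm is seen.

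The change needs no participants, visits or data. What is given up is the simple matching intervals (step-down) or exactness under unequal dropout (Tukey-Kramer), together with some of Bonferroni's margin below 5%. The power statement quotes 0.008 as well, so it should be reworded to name the chosen procedure and to say whether its power is for a given pair or for any pair.
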